11.0 Laboratory Assessments

Study associated laboratory assessments (blood and urine) will be collected at time points specified in Study Procedures Table (Attachment 1) and analyzed by a local laboratory with the exception of the urine dipstick assessments which will be collected and analyzed onsite

A total of 36 mL of blood will be collected for screening assessments (Visit 1), 30 mL of blood will be collected at Visits , 6, and 10.

Laboratory assessments to be completed:

1. complete blood count with differential (CBC w/diff)
2. comprehensive metabolic panel (CMP)
3. uric acid level
4. creatinine clearance
5. calcium
6. lipid panel
7. hemoglobin A1c (HgbA1c)
8. thyroid stimulating hormone level (TSH)
9. pregnancy test (urine)
10. urine toxicology screen
11. urinalysis
12. hepatitis panel
13. serological assessment of antibodies to HSV1
14. inflammatory markers (HSV1, HSV2, EBV, HHV6, CMV, CRP, VZV, and Toxoplasmosis)

*All clinically significant abnormal laboratory findings subsequent to randomization will be repeated at appropriate intervals to establish resolution or until appropriate clinical follow-up can be established.

Serological Assessment of Antibodies to HSV1:

A serological assessment of antibodies to HSV1 will be completed by a central laboratory, Mayo Clinic Mayo Medical Laboratories, and results will be reported during the screening period prior to randomization for each subject. Results will be sent electronically to Indiana University Department of BioStatistics who will release the result to identified unblinded study personnel at each study site. The unblinded study personnel will be responsible for randomizing subjects to study treatment according to the stratified randomization block.

Inflammatory Markers

Inflammatory markers (HSV1, HSV2, EBV, HHV6, CMV, CRP, VZV, and Toxoplasmosis) will be assessed with methods previously described.²⁷ These serologic assessments will be performed centrally in [name] laboratory at the Johns Hopkins University School of Medicine. These blood samples will be de-identified at sites prior to sending for analysis. Study site investigators will remain blinded to the results of these assessments until after the trial has been completed.

Optional Repository Participation

An additional 4ml of whole blood will be collected (2ml serum) and sent to [name] at Johns Hopkins University School of Medicine repository from all consented subjects in the main study (collected at screening) for later unspecified inflammatory marker analyses related to psychiatric disorders. Subjects may refuse to participate in the repository without consequence to their participation in the main study. These samples will be given a unique subject number linking the main study subject number to the repository subject number at the site level. Samples will be sent to the Johns Hopkins University School of Medicine repository using the repository subject

number only. Non-identifying demographic information will be submitted to Johns Hopkins University School of Medicine repository at the time of sample submission. The code linking subject to repository subject number will be destroyed by sites at the end of the main study, truly de-identifying the samples. Subjects will be able to request sample destruction from the Johns Hopkins University School of Medicine repository by formal request to the main study site until the time the identifying code is destroyed at the site level.

12.0 Study Medication/Treatment

Valacyclovir hydrochloride and matching placebo capsules will be used as study medication for this study. Placebo capsules will look like valacyclovir capsules, with matching shape, taste, and color. Subjects will be instructed to take 6 capsules of study medication daily.

The investigator or his/her designee is responsible for explaining the correct use of the study medication to the subjects, verifying subject understanding and agreement, maintaining accurate records of dispensing and collection, and destroying all unused medication according to their pharmacy standard operating procedures at the end of the study. Subjects will be instructed to contact the investigator as soon as possible if they have a complaint or problem with the study medication so that the situation can be assessed.

Method of Assignment to Treatment

Subjects who meet all criteria for enrollment will be 1:1 randomized in a double-blind fashion to adjunctive treatment with valacyclovir or placebo at Visit 2. Assignment to treatment groups will be determined by a computer-generated random sequence provided to sites by an unblinded biostatistics team at Indiana University. To minimize potential imbalance among treatment groups of factors that may influence efficacy outcomes, a stratified random assignment of subjects to therapy will be used to insure equal representation of HSV1 positive and negative subjects in the placebo and valacyclovir arms. The stratification factors used for this study include the investigative site.

Compounding and Pharmacy Oversight

Study medications will be sent to study sites at regular intervals from the University of Iowa which is contracted by Indiana University for preparation and shipping study medication for this study.

Study medication will be purchased directly through Indiana University. University of Iowa pharmacy will over-encapsulate the valacyclovir and create matching placebo capsules. Study medication will be stored according to the details on the product label (59° to 77° F).

Dosing

The dosing used in this study is 3 capsules of either valacyclovir or /placebo by mouth twice per day, given without regard to meals. Each valacyclovir capsule will contain 500 mg of active ingredient for a total daily dose of 3 grams per day. Dose reductions of 2 capsules per day will be permitted to address adverse events at the discretion of the site investigator.

Dispensing

Dispensing method will be chosen by each site and will include one of the following options:

Option 1: Bulk Supply/Local Pharmacy

Each investigative site will identify their local pharmacy used for dispensation to subjects. Indiana University will provide randomization numbers to each site. The local pharmacy will be responsible for randomizing subjects to groups and dispensing medication to subjects according to their local standard operating procedures. Each investigative site will remain blinded, but each site's pharmacy will hold their subjects treatment assignment which may be broken in the case of an emergency.

Option 2: Individual Blinded Packages/Unblinded Site Personnel

University of Iowa will label and package medication into individual packages for subject assignment by unblinded site personnel. Indiana University will provide randomization numbers to each site. Each investigative site will identify their unblinded site personnel to be used for package assignment to subjects. The unblinded site personnel will be responsible for randomizing subjects to groups and dispensing medication to subjects according to their local standard operating procedures. Each investigative site will remain blinded, but the unblinded site personnel will hold their subjects treatment assignment which may be broken in the case of an emergency.

Compliance

Compliance will be assessed at each visit by direct questioning and medication count of unused medication and packaging to be returned at each visit. Adequate study medication dispensing records will be obtained.

13.0 Concomitant Medication

The list of excluded medications and procedures is provided in Attachment 2.

Benzodiazepine Equivalents Use

The use of benzodiazepines/hypnotics/anxiolytics is permitted during the study (all study periods). Benzodiazepines should not be administered 8 hours before psychiatric evaluations during all study periods. Every effort should be made to use the smallest amount possible. Benzodiazepines should only be taken "as needed" (PRN), and not as a standing dose unless the subject has been receiving a stable dose of a benzodiazepine/hypnotic/ anxiolytic for at least 30 days immediately prior to Visit 1. Benzodiazepine usage, however, must be recorded in mg with valid start and stop dates, and should not be recorded with a "PRN" frequency.

Table 1 lists the only allowed benzodiazepine equivalents to be prescribed in this study. Subjects should not exceed the maximum daily dose of any individual agent as specified in Table 1.

The use of multiple benzodiazepines concurrently is discouraged.

Table 1. List of Benzodiazepine Equivalents

Benzodiazepine	Max Daily Dose
Lorazepam	6 mg
Temazepam	30 mg
Diazepam	30 mg
Flunitrazepam	6 mg
Phenazepam	2 mg
Clonazepam	1.5 mg
Nitrazepam	5 mg
Flurazepam	30 mg
Triazolam	0.25 mg
Oxazepam	60 mg
Chloral hydrate	2000 mg
Chlordiazepoxide	75 mg
Alprazolam	3 mg
Zolpidem	10 mg
Eszopiclone	3 mg

Anticholinergic Therapy

The use of anticholinergic medications is permitted during the study (all study periods) (Table 3). PRN anticholinergics should not be administered 8 hours before psychiatric evaluations during all study periods. Every effort should be made to use the smallest amount possible. Anticholinergic medications should only be taken “as needed” (PRN), and not as a standing dose unless the subject has been receiving a stable dose of the anticholinergic medication for at least 30 days immediately prior to randomization. In those cases the anticholinergic medication should be taken at the regularly scheduled time. Anticholinergic medication usage, however, must be recorded in mg with valid start and stop dates (and frequency if scheduled), and should not be recorded with a “PRN” frequency. If multiple anticholinergic medications are in use then use the equivalency table to determine maximum allowable daily dose (Table 4).

Table 3. Allowed Anticholinergic Medication

Anticholinergic	Maximum Daily Dose
Benzotropine mesylate	6 mg
Biperiden	6 mg
Procyclidine	15 mg
Trihexyphenidyl (Benzhexol)	15 mg

Table 4. Estimated Anticholinergic Equivalency

Anticholinergic	Estimated Anticholinergic Equivalency
Benztropine	1 mg
Biperiden	1 mg
Diphenhydramine	67 mg
Procyclidine	2.5 mg
Trihexyphenidyl	2.5 mg

14.0 Adverse Events and Reporting

For the purposes of collecting and evaluating all information found during this clinical study, an **adverse event** is any undesirable or unexpected experience that occurs after informed consent has been obtained without regard to the possibility of a causal relationship, and without regard to treatment group assignment. All adverse events will be documented and all serious adverse events will be reported following local IRB requirements.

For non-serious adverse events, research staff will question each subject and will document the occurrence and nature of presenting condition(s). Pre-existing condition(s) and any change in the pre-existing condition(s) will be documented and/or the occurrence and nature of any adverse event.

A **serious adverse event** is any adverse drug experience occurring at any dose that: results in death, is life threatening, results in inpatient hospitalization or prolongation of existing hospitalization, results in a persistent or significant disability/incapacity, or results in congenital anomaly/birth defect.

All serious adverse events will be documented and reported to appropriate regulatory bodies.

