Valacyclovir is the oral L-valyl ester prodrug of acyclovir and is converted to acyclovir via first-pass hepatic metabolism. Valacyclovir's properties have been reviewed.^{15,16} Valacyclovir is approved by the United States Food and Drug Administration (FDA) for the treatment of herpes zoster and genital herpes and for the suppression of herpes virus infections including HSV-1.¹⁷ Acyclovir is phosphorylated by viral thymidine kinases to its active form. This form inhibits DNA synthesis through competitive inhibition of viral DNA polymerase. Maximum plasma concentration of acyclovir is achieved in 1-3 hours after oral administration and the elimination half-life is 2.5-3.6 hours. Acyclovir is predominantly eliminated by glomerular filtration and tubular secretion. Valacyclovir is widely prescribed and considered to be relatively safe and well tolerated.¹⁷

Risks and Discomforts Associated with valacyclovir:

In clinical trials in adult patients, adverse events commonly observed more frequently with valacyclovir than placebo and at a rate of $\geq 10\%$ are:

- Headache
- Nausea
- Stomach pain

In clinical trials in adult patients, adverse events observed more frequently with valacyclovir than placebo and occurring at a rate of $<10\%$ but $>1\%$ are:

- Dizziness
- Painful periods (females only)
- Joint pain
- Depression
- Vomiting
- Fatigue (sleepiness)
- Rash
- Low blood cell counts (neutrophil and platelet)
- Inflammation of the nose and throat
- Upper respiratory tract infection
- Increased liver enzyme levels (signs of liver damage)

The following are rare but are considered serious adverse reactions:

- **Thrombotic Thrombocytopenic Purpura/Hemolytic Uremic Syndrome (TTP/HUS):** This is a blood clotting problem which can be fatal. Cases of TTP/HUS, in some cases resulting in death, have been reported in patients who have advanced HIV disease and in patients who have had transplants and are on valacyclovir
- **Acute Renal Failure (kidney failure):** cases have been reported in elderly patients, those with underlying kidney disease, patients taking other drugs that may cause damage to the kidneys, and patients without adequate hydration (dehydrated)
- **Central Nervous System Effects:** agitation, hallucinations, confusion, delirium, seizures, and encephalopathy (brain swelling) have been reported in adult patients who received higher-than-recommended doses of valacyclovir¹⁷

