The recommended dosage for suppression of recurrent genital herpes is 500-1000 mg taken once daily. Safety and efficacy of this regimen have been established for patients receiving these doses for up to 1 year. In a large-scale, 1 year, dose finding study for valacyclovir use in genital herpes suppression, 5.1% of all patients enrolled had discontinued their therapy because of an adverse event.¹⁸ The percentages for discontinuing therapy were similarly distributed among the 6 treatment groups of the study (4 valacyclovir groups at 250 mg, 500 mg, 1 g once daily, or 250

mg twice daily; 1 acyclovir group at 400 mg twice daily; and 1 placebo group).¹⁸ Valacyclovir adverse events reported in this study include headache, rhinitis, infection, flu-like syndrome, pharyngitis, nausea, back pain, diarrhea, abdominal pain, sinusitis, and dyspepsia. The frequency of these adverse events to valacyclovir was similar to that observed in patients receiving placebo. Abnormal laboratory tests for anemia, leukopenia, thrombocytopenia, AST (SGOT), and serum creatinine were also evaluated and the frequency of adverse events to valacyclovir was similar to that observed in patients given placebo and no association was observed between valacyclovir treatment and any abnormal laboratory test.¹⁸ Doses up to 8 grams per day were used in pre marketing studies.¹⁷ The study medication dose for this study will be 1.5 g by mouth, twice daily. This dose is identical to the University of Pittsburgh pilot trial (see below) and it is adequate for suppressive HSV-1 therapy.¹⁷ We are proposing to use the dose of 1.5 g twice daily because this was the dose shown to be effective in the Prasad study.

Pilot trial of valacyclovir augmentation in early course schizophrenia

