10.0 Criteria for Repeat Assessments, Rescreening, and Discontinuation

Repeat Assessments

Screening assessments can be repeated within the screening window under the same screening number with the exception of eligibility criteria related rating scales/questionnaires. Subject diagnosis confirmation will not be repeated.

Rescreening

Subjects who screen fail may be rescreened one time, under a new screening number. If a subject is rescreened, all screening assessments (with the exception of the diagnosis confirmation) must be repeated and the stability criteria timelines must be met.

Discontinuation

Subjects will be discontinued under the following circumstances:

1. Study Medication Non-Compliance: Significant noncompliance is defined as missing seven or more consecutive days of study medication or more than 24 cumulative days of study medication during the entire study.
2. Subjects who have the following lab values while on study medication:
 - Liver transaminase levels >3 times the ULN
 - Hemoglobin <9
 - White blood cells <1500
 - Serum creatinine >1.5
3. Subjects who develop moderate or severe renal impairment as defined by CrCl <50 ml/min (measured by the Cockcroft-Gault equation) while on study medication
4. Female subjects who become pregnant while on study medication
5. Subjects who require more than 50% increase in their dose of antipsychotic medication OR the addition of a new antipsychotic medication will be reviewed by the principal investigator and discontinuation will be addressed on a case-by-case basis as clinically indicated.
6. Subjects who require treatment with any excluded concomitant medications (See Attachment 2)

If a subject discontinues from the study, discontinuation assessments will be at the discretion of the investigator.

A subject may withdraw from the study medication at any time at his/her own request, or may be withdrawn at any time at the discretion of the investigator for safety, behavioral, or administrative reasons.

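### The serious-adverse-event definition has no criterion for medically important events, so reactions the protocol itself calls serious can be classed non-serious in outpatients

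*Combined protocol and SAP*

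**What the plan says.** Section 14.0 (Adverse Events and Reporting) defines a serious adverse event by outcome. The event is serious if it "results in death, is life threatening, results in inpatient hospitalization or prolongation of existing hospitalization", or if it "results in a persistent or significant disability/incapacity, or results in congenital anomaly/birth defect". The list ends there. The same section has every adverse event documented, but it states reporting to the IRB and to regulatory bodies for serious events only.

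Section 2.0 (Scientific Background and Rationale) introduces three classes of reaction to valacyclovir with the words "The following are rare but are considered serious adverse reactions". They are TTP/HUS, acute renal failure and central nervous system effects. On the third class it says that "agitation, hallucinations, confusion, delirium, seizures, and encephalopathy (brain swelling) have been reported in adult patients who received higher-than-recommended doses of valacyclovir".

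Four other provisions bear on what happens to an event that is not classed as serious:

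- Section 9.0 has clinically significant laboratory, examination and clinical-interview changes recorded as adverse events with a causality assessment. It also requires follow-up of events that are serious or that led to discontinuation.
- Section 10.0 discontinues subjects who cross stated renal and other laboratory limits.
- Section 15.0 gives each site a DSMB that reviews adverse events at least bi-annually, with its report going to the IRBs. It sends unanticipated events to the lead investigators at once.
- Section 16.0 compares event rates between arms for all events, serious events, psychiatric events and events by organ system.

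**The concern.** Sections 2.0 and 14.0 do not use the word serious in the same way. Section 2.0 attaches it to kinds of reaction; Section 14.0 attaches it to five outcomes. A reaction of a kind named in Section 2.0 that reaches none of those outcomes is non-serious for reporting and for analysis. This is the result of following a stated rule, not of missing detail.

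Two things are at stake. The first is individual reporting: a drug reaction the protocol foresees and regards as serious would not go to the IRB or regulators as a single case. The second is secondary aim 4 (Section 3.0), on tolerability and safety: the serious-event line in the safety table, where a reader would look first for these reactions, could omit some of them.

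**Working it through.** No figure in the plan is involved, so the check sets the sections side by side.

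**Step 1. Test outpatient cases against the five criteria in Section 14.0** (death; threat to life; admission or longer admission; lasting disability; birth defect).

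| Case, managed without admission | Criterion met? | Class under Section 14.0 |
|---|---|---|
| Isolated seizure, full recovery | None, unless judged life threatening | Non-serious |
| Confusion or hallucinations that resolve | None, unless judged life threatening | Non-serious |
| Acute renal failure | None, unless judged life threatening or lastingly disabling | Can be non-serious |
| TTP/HUS | Section 2.0 says it can be fatal, so the life-threatening or admission criterion would often apply | Usually serious |

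The gap is therefore real for an isolated seizure, for confusion and for a renal event that does not threaten life. It is small for TTP/HUS, and encephalopathy would also often meet a criterion.

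**Step 2. Follow a non-serious event through the plan.**

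- Documentation (Section 14.0): yes. Changes in pre-existing conditions are also recorded, which covers worsening psychosis.
- Individual report to IRB and regulators (Section 14.0): not required, since the reporting sentences cover serious events only.
- Immediate route (Section 15.0): it covers unanticipated events. A reaction listed in Section 2.0 is anticipated, so this route does not clearly apply.
- Causality (Section 9.0): assessed for clinically significant laboratory, examination and interview findings. The interview named there is the suicidality interview, so whether it catches confusion or new hallucinations is arguable.
- Follow-up (Section 9.0): required if the event led to discontinuation. That includes renal events crossing the Section 10.0 limits, but follow-up is not serious-event reporting.
- Periodic review (Section 15.0): yes, by the site's DSMB.
- Analysis (Section 16.0): counted among total events and in the psychiatric or organ-system groups; absent from the serious group.

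**Step 3. State what is lost.** Two things: the individual serious-event report, and the event's place in the serious-event comparison.

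**Step 4. Size.** Section 2.0 gives no rate for these reactions beyond calling them rare. The number of events moved from serious to non-serious cannot be computed from the documents.

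**The case against.** The strongest case against the point is that the plan already catches these events elsewhere. All adverse events are documented, the DSMB sees them, and Section 16.0 compares psychiatric and organ-system events by arm, so an arm difference could show there whatever the seriousness label. Section 2.0 is a background list of reaction types, while Section 14.0 classifies single cases by outcome, and the two need not match word for word. The population also lowers some of the risk: ages 18 to 40, with known HIV, creatinine clearance below 60 ml/min, and systemic aminoglycosides and vancomycin all excluded.

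Much of this stands. A reader might infer that these reactions go unreported; the documents do not support that, given the routes traced above. A reader might also infer that all three reaction classes routinely escape the definition; the life-threatening and admission criteria make that unlikely for TTP/HUS and for many renal cases.

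What the objection does not remove is the loss of individual reporting. The periodic route is site by site: 175 subjects over 5 sites is 175/5 = 35 per site on average, so a rare event is seen by one board at a time. If bi-annually means twice a year, reviews may be 52/2 = 26 weeks apart, longer than the 16-week treatment period. In the Section 16.0 groups, a seizure or a confusional episode is pooled with commoner events such as headache, or with symptoms of the illness itself. The exclusions address risk factors that Section 2.0 names for TTP/HUS and renal failure; it names no comparable patient risk factors for the central nervous system effects.

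**Conclusion.** The point holds in a limited form. The five outcome criteria leave out medically important events, so some reactions that Section 2.0 calls serious can be classed non-serious when managed in outpatients. They then miss individual serious-event reporting and the serious-event comparison, while still being documented, periodically reviewed and counted elsewhere. This rests on Section 14.0 being applied as written, and on the event not being judged life threatening or lastingly disabling. The size of the effect is unknown.

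Two stronger readings are tempting and are not supported:

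- **Dose.** A reader might infer that the central nervous system warning applies to this trial because the regimen is given "for a total daily dose of 3 grams per day" while "The recommended dosage for suppression of recurrent genital herpes is 500-1000 mg taken once daily": 3000/1000 = 3 and 3000/500 = 6 times. That comparison is with one indication only. Section 2.0 does not say which recommended dose its warning refers to, and it also reports pre-marketing use of up to 8 g per day. The ratio does not show that the warning applies.
- **Causality.** A reader might infer that nobody asks whether study drug caused new psychotic symptoms, because Section 10.0 says of antipsychotic increases that "discontinuation will be addressed on a case-by-case basis as clinically indicated". That is a discontinuation rule and does not replace adverse-event recording; Section 9.0 separately calls for causality to be assessed for the findings it covers.

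**What to change.** Reconcile Sections 2.0 and 14.0. Add to the Section 14.0 definition a sixth criterion: an event that is medically important in the investigator's judgement. State beside it that the reactions listed as serious in Section 2.0, when new or worse than the subject's baseline, are to be considered under that criterion. The reference to baseline matters because agitation and hallucinations also belong to the illness under study.

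The change should stop there. Making every laboratory discontinuation, or every new or worse episode of agitation or hallucinations, automatically serious could fill the category with illness events and blur the comparison it is meant to protect.

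The cost is a few lines in Section 14.0 and a small number of additional serious-event reports, some of which may later be judged unrelated to study drug. No new visit, procedure or analysis category is needed, and no dose or treatment rule changes.
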